Rationale: This trial is intended to test a new formulation of insulin lispro (LY900014) in patients with type 1 diabetes mellitus (T1DM) using continuous subcutaneous insulin infusion (CSII). The use of LY900014 will be compared to insulin lispro (Humalog® U-100; Reference formulation) when given as a standard dual-wave bolus dose or as a standard (1.5 U/minute) single-wave bolus dose on both Days 1 and 3 and as a rapid (15 U/minute) or standard (1.5 U/minute) single-wave bolus dose on Day 2, with a breakfast meal test using an insulin pump. In addition, rapid versus standard dual-wave bolus doses and rapid versus standard single-wave bolus doses will be compared during the lunch and dinner meals, respectively, using the assigned treatment (LY900014 or Humalog) for that period. Humalog is already marketed and used in diabetes treatment, and its efficacy and safety as a single insulin preparation is well known.

Objectives/Endpoints:

Primary Objectives	Endpoints
To evaluate the difference in insulin lispro PK when LY900014 and Humalog are administered as different test bolus doses with an insulin pump to patients with T1DM during a breakfast meal test	AUC, C_{max} , T_{max} , early 50% T_{max} , and late 50% T_{max}
Secondary Objectives	Endpoints
To evaluate the sustainability of any difference in insulin lispro PK of LY900014 and Humalog over 3 days when administered as different test bolus doses with an insulin pump to patients with T1DM during a breakfast meal test	AUC, C_{max} , T_{max} , early 50% T_{max} , and late 50% T_{max}
To evaluate the difference in GD response when LY900014 and Humalog are administered as different test bolus doses with an insulin pump to patients with T1DM during a breakfast meal test	Δ AUC
To compare the durability of GD response over 3 days when LY900014 and Humalog are administered as different test bolus doses with an insulin pump to patients with T1DM during a breakfast meal test	Δ AUC

Abbreviations: AUC = area under the concentration versus time curve; C_{max} = maximum concentration; early 50% T_{max} = time to early half-maximal concentration; GD = glucodynamics; late 50% T_{max} = time to late half-maximal concentration; PK = pharmacokinetics; T1DM = type 1 diabetes mellitus; T_{max} = time to maximum concentration.

Summary of Study Design: This is a single-site, 4-period, patient- and investigator-blind, randomized, crossover study in patients with T1DM to evaluate the insulin lispro pharmacokinetic (PK) and glucodynamic (GD) characteristics of LY900014 (Test) over 3 days with CSII compared with that of Humalog (Reference) using a

██████████
C
C
I

Each patient will be randomized to 1 of 4 treatment sequences comprising CSII of LY900014 or Humalog, with different combinations of the modes of administration of the bolus doses relative to the breakfast, lunch, and dinner meals using an insulin pump. The modes of administration are as follows:

- Mode 1: bolus dose is administered as a standard dual-wave bolus (50% immediate bolus delivery [speed = 1.5 U/minute] and 50% as a square wave over 3 hours)
- Mode 2: bolus dose is administered as a standard single-wave bolus (speed = 1.5 U/minute)
- Mode 3: bolus dose is administered as a rapid single-wave bolus (speed = 15 U/minute)
- Mode 4: bolus dose is administered as a rapid dual-wave bolus (50% immediate bolus delivery [speed = 15 U/minute] and 50% as a square wave over 3 hours)

A mixed-meal tolerance test (MMTT) will be administered at breakfast as an individually standardized solid test meal on Day 1 and Day 3 and as a high-glycemic index test meal on Day 2. The assigned treatment will be administered as a bolus dose at time 0 relative to the start of each breakfast test meal via 3 different modes: Modes 1, 2, and 3.

An individually standardized solid lunch will be administered on Days 1, 2, and 3. The assigned treatment will be administered as standard (Mode 1) or rapid (Mode 4) dual-wave bolus doses at time 0 relative to the start of each lunch meal.

An individually standardized dinner will be administered on Days 1 and 2. The assigned treatment will be administered as standard (Mode 2) or rapid (Mode 3) single-wave bolus doses at time 0 relative to the start of each dinner meal.

Treatment Arms and Duration: Patients will be randomly assigned to 1 of 4 dosing sequences; each sequence will have 4 periods. Patients will be administered bolus doses of LY900014 or Humalog during the 3-day inpatient stay for each study period and bolus doses of Humalog for the lead-in and outpatient time periods.

Number of Patients: Initially, 24 patients will be enrolled to target approximately 20 patients to complete all 4 periods of the study. Patients who drop out may be replaced, up to a maximum of 30 total patients enrolled, to ensure 20 completers; the replacement patient will adopt all assigned treatments of the original patient's randomization schedule and complete all 4 study periods.

Statistical Analysis:

Primary statistical analyses will be conducted on the set of patients receiving at least 1 dose of the study drug to which they are randomized. Patients who complete at least 1 MMTT and have measurable insulin lispro concentrations will be included in the analysis dataset for the PK analyses. Patients who receive at least 1 dose of study drug and have evaluable GD data will be included in the analysis set for the GD analyses.

Sample Size: Twenty completing patients will provide approximately 80% power to demonstrate a 25% decrease in the time to early half-maximal concentration (early 50% T_{max}) between LY900014 and Humalog. Testing will be done at an α -level of 0.1 with a 2-sided confidence interval (CI). The variability was estimated as approximately 35.9% coefficient of variation of within-subject variability for early 50% T_{max} .

Safety: All treatment- (investigational product and Humalog noninvestigational product) and procedure-related adverse events (AEs) will be listed, and if the frequency of events allows, safety data will be summarized using

descriptive methodology. The incidence of symptoms for each treatment will be presented by severity and by association with investigational product as perceived by the investigator. The number of investigational product-related serious AEs (SAEs) will be reported. Safety parameters that will be assessed include safety laboratory parameters and vital signs. The parameters will be listed and summarized using standard descriptive statistics.

Pharmacokinetics: PK analyses will be conducted using standard noncompartmental methods of analysis. Serum insulin lispro concentrations will be used to calculate several PK parameters, including time to maximum concentration (T_{max}), early 50% T_{max} , time to late half-maximal concentration (late 50% T_{max}), maximum concentration (C_{max}), area under the plasma concentration versus time curve (AUC) from time 0 to 15 minutes postdose (AUC[0-15min]), AUC from time 0 to 30 minutes postdose (AUC[0-30min]), AUC from time 0 to 1 hour postdose (AUC[0-1h]), AUC from time 0 to the last recorded time (AUC[0- t_{last}]), and AUC from time 0 to 5 hours postdose (AUC[0-5h]).

Log-transformed insulin lispro T_{max} , early 50% T_{max} , late 50% T_{max} , C_{max} , and AUC estimates will be evaluated to estimate geometric means, ratios of geometric means of insulin lispro within LY900014 to Humalog, and the corresponding 90% CIs of the ratios.

The statistical model for Days 1 and 3 breakfast meal tests will include treatment (4 combinations of treatment and bolus administration mode), period, day-within-period, and treatment-by-day-within-period interaction as fixed effects and patient as a random effect. A separate analysis model will be used for the Day 2 breakfast meal test, including treatment (4 combinations of treatment and bolus administration mode) and period as fixed effects and patient as a random effect. For the primary inference, insulin lispro administered from LY900014 will be concluded to have a significantly decreased early 50% T_{max} relative to Humalog if the upper confidence bound of the 2-sided 90% CI of the ratio of geometric means of the early 50% T_{max} is <1 . As a sensitivity analysis, early 50% T_{max} will be analyzed using the Wilcoxon signed-rank test.

Glucodynamics: Data will be analyzed for the patients during each MMTT. The change from baseline values for each patient will be calculated. Incremental change from baseline glucose AUC values will be calculated during a 5-hour meal test.

Summary statistics will be presented by treatment and by bolus dose administration mode (all 4 combinations of treatment) for Days 1 and 3 and Day 2, separately. The same statistical model and comparisons used to analyze the PK parameters will be used to analyze the GD parameters on the original scale (not log-transformed) using Fieller's theorem.

Exploratory Continuous Glucose Monitoring: The continuous glucose monitoring (CGM) outcome variables (for example, incremental change from baseline AUC[0-5h], the change from baseline 1- and 2-hour excursions) will be derived based on the raw data collected from the individualized standardized lunch meals on Days 1, 2, and 3 and from the individualized standardized dinner meals on Days 1 and 2.

Immunogenicity: The relationship between the status (positive or negative) of treatment-emergent anti-insulin lispro antibodies and treatment-emergent AEs (TEAEs) will be assessed. Likewise, the relationship between the status of treatment-emergent antibodies and the PK parameters and GD response to insulin lispro may also be assessed.

2. Schedule of Activities

Study Schedule Protocol I8B-MC-ITSC

Procedure	Screen ^a Days -28 to -8	Lead-In Days -7 to -1	Periods 1 to 4				ED/ FUa,b	Comments
			Day -1	Day 1	Day 2	Day 3		
Informed consent	X							At least 1 day before screening procedures. Screening procedures should take place no later than 28 days after signing the informed consent.
Physical examination/medical assessment	X		X			Before discharge from CRU	X	Physical examination and medical history at screening. Thereafter, medical review and targeted examination, as appropriate, including review of patient diary.
AE and concomitant medication	X		X	X	X	X	X	
Height and weight	X						X	Height will be measured at screening only.
Eligibility assessment	X		X					Meal test exclusion criteria (Section 6.3.1) will be reviewed on Day -1 at admittance to the CRU.
Lead-in activities		X						Patients will switch from their short-acting insulin used before the start of the study to Humalog; patients will continue to use their own pump to administer Humalog. A patient diary will be provided for recording dosing and any information as required by the investigator (refer to Section 5.1 for a detailed description).
Training		X				X		Diabetes training will include dose calculation for short-acting insulins; correct self-monitoring of plasma glucose; and interpretation of results, symptoms, and treatment of hypoglycemia.
Admission to CRU			X					Will be admitted to CRU in the early evening (approximately 5:00 PM).
Discharge from CRU						X		Patients will be discharged from the CRU at least 5 hours after the start of the lunch meal.

Procedure	Screena Days -28 to -8	Lead-In Days -7 to -1	Periods 1 to 4				ED/ FUa,b	Comments
			Day -1	Day 1	Day 2	Day 3		
Insert CGM			X				The CGM system will be inserted before the start of the Day -1 standardized dinner.	
Standardized dinner			X				Approximately 7:00 PM and should be consumed within 20 minutes. Identical to the standardized test dinner served on Days 1 and 2.	
Catheter insertion/change			X			X	Day -1: after the standardized dinner. Day 3: after the lunch meal procedures (blood draws and medical assessments) are completed (approximately 5 hours after the start of the lunch meal), unless the patient stays at the clinic until that evening (approximately 5:00 PM) for Day -1 procedures for next period; then the new catheter will be inserted after the standardized dinner (Day -1 for the following period).	
Run-in/stabilization of glucose				X (approximately 1:00 AM)		X (approximately 1:00 AM)	From 7 hours to 30 minutes before dosing: infusion of glucose (dextrose solution) or insulin [REDACTED] to target a plasma glucose concentration of 126 mg/dL (7.0 mM). Run-in/stabilization of glucose will begin at approximately 1:00 AM. Plasma glucose concentrations will be monitored approximately every 30 minutes.	
Glucose monitoring before Day 2 meal test					X		After completion of the standardized dinner to 30 minutes before dosing: plasma glucose concentrations will be monitored approximately every hour.	

Procedure	Screena Days -28 to -8	Lead-In Days -7 to -1	Periods 1 to 4				ED/ FUa,b	Comments
			Day -1	Day 1	Day 2	Day 3		
Glucose monitoring throughout inpatient period			X	X	X	X	Regular monitoring of blood glucose using the CCI (approximately every 2 hours) will also be performed during the complete inpatient period outside of the breakfast meal test procedures and includes predose before the standardized lunch and dinner.	
Treatment administration (LY900014 or Humalog)			X	X	X	X	Day -1 prandial Humalog shall be administered using the patient's own personal pump. After the standardized dinner the patient will switch to the CCI; the reservoir will be filled with the assigned study treatment (LY900014 or Humalog) by qualified staff. Study treatment will be administered continuously via a basal infusion and via a bolus dose immediately before each breakfast test meal and standardized lunch meal (Days 1, 2, and 3) and before each standardized dinner meal (Days 1 and 2 only), which should follow within 1 minute of dosing.	
Breakfast test meals (refer to Sections 6.3.1.1 and 6.3.1.2)				X (MMTT)	X (high-glycemic index meal test)	X (MMTT)	Breakfast (Days 1, 2, and 3) will be given immediately after dosing (approximately 8:00 AM) and should be consumed within 20 minutes on Days 1 and 3 and within 15 minutes on Day 2.	
Standardized test lunch (refer to Section 6.3.1.3)				X	X	X	Approximately 1:00 PM and at least 5 hours after the start of the breakfast meal; the meal should be consumed within 20 minutes.	
Standardized test dinner (refer to Section 6.3.1.3)				X	X		Approximately 7:00 PM and at least 5 hours after the start of the lunch meal; the meal should be consumed within 20 minutes.	

Procedure	Screen ^a Days -28 to -8	Lead-In Days -7 to -1	Periods 1 to 4				ED/ FU ^{a,b}	Comments
			Day -1	Day 1	Day 2	Day 3		
Remove CGM						X		After the Day 3 lunch meal procedures are completed (approximately 5 hours after the start of the lunch meal), the CGM system will be removed.
Vital signs ^c (minutes)	X		X	X (predose, 30, 120)	X (predose, 30, 120)	X (predose, 30, 120, and before discharge from CRU)	X	Blood pressure and pulse rate should be measured after at least 5 minutes supine; body temperature at screening only. Time is referenced to bolus dose of insulin lispro (LY900014 or Humalog) for the breakfast meal tests, that is, time 0.
12-lead ECG ^c	X			X (predose, Period 1 only)		X (predose, Period 1 only)	X	Single ECGs only. ECGs should be recorded before collecting any blood for safety or PK tests.
Clinical laboratory tests ^c	X			Period 1 only (predose)			X	Details in Appendix 2 (Clinical Laboratory Tests).
Alcohol breath test			X					May be repeated before every CRU admission. The alcohol breath test is included in the Day -1 eligibility assessment.
Pregnancy test/urine drug screen	X		X				X	Pregnancy test will be taken for female patients only. Serum pregnancy test at screening. Urine pregnancy test for all other visits.
Insulin lispro PK sampling (minutes)				-15, 0, 5, 10, 15, 20, 25, 30, 35, 40, 45, 50, 55, 60, 70, 90, 120, 150, 180, 240, 300	-15, 0, 5, 10, 15, 20, 25, 30, 35, 40, 45, 50, 55, 60, 70, 90, 120, 150, 180, 240, 300	-15, 0, 5, 10, 15, 20, 25, 30, 35, 40, 45, 50, 55, 60, 70, 90, 120, 150, 180, 240, 300		Time is referenced to the start of the administration of the bolus dose of insulin lispro (LY900014 or Humalog) for the breakfast meal tests, that is, time 0.

Procedure	Screen ^a Days -28 to -8	Lead-In Days -7 to -1	Periods 1 to 4				ED/ FU ^{a,b}	Comments
			Day -1	Day 1	Day 2	Day 3		
Plasma glucose monitoring with Super GL glucose analyzer (minutes)				-30, -15, 0, 10, 20, 30, 40, 50, 60, 70, 80, 90, 100, 110, 120, 135, 150, 165, 180, 195, 210, 225, 240, 300	-30, -15, 0, 10, 20, 30, 40, 50, 60, 70, 80, 90, 100, 110, 120, 135, 150, 165, 180, 195, 210, 225, 240, 300	-30, -15, 0, 10, 20, 30, 40, 50, 60, 70, 80, 90, 100, 110, 120, 135, 150, 165, 180, 195, 210, 225, 240, 300		Time is referenced to the start of the administration of the bolus dose of insulin lispro (LY900014 or Humalog) for the breakfast meal tests, that is, time 0.
VAS and insertion-site assessments (minute)				0 ^d , 20, 40, 60, 120, 180, 240, 300	0 ^d , 20, 40, 60, 120, 180, 240, 300	0 ^d , 20, 40, 60, 120, 180, 240, 300		Time is referenced to dose of insulin lispro (LY900014 or Humalog) for the breakfast test meals.
Assessment of insulin delivery experience						X		Subjects will be asked to provide the overall acceptability of their insulin delivery experience, either prior to CRU discharge or after completing Day 3 lunch procedures for each period.
Biomarker sample ^c (PGx)				Period 1 only (predose)				
Sample for immunogenicity ^c				Period 1 only (predose)			X	Additional samples may be collected if there is a possibility that an AE is immunologically mediated.

Abbreviations: AE = adverse event; CGM = continuous glucose monitoring; CRU = clinical research unit; ECG = electrocardiogram; ED = early discontinuation; FU = follow-up; MMTT = mixed-meal tolerance test; PK = pharmacokinetics; VAS = visual analog scale.

Note: Interim telephone visits may occur at any time during the outpatient periods, as determined by the investigator, to review the safety and well-being of the patient.

- a Patients should be fasted for at least 8 hours before the start of screening and follow-up (or early discontinuation) activities. Patients may consume up to 20 g of carbohydrates to treat or prevent hypoglycemia during the fasting periods.
- b Within 7 to 14 days after last dose or early discontinuation.
- c Predose is defined as the predose for the breakfast test meal only. Predose measurements should be performed within approximately 2 hours before the planned dosing time.
- d The VAS at the 0-minute time point is to be performed as soon as practicably possible after the start of the dosing for the breakfast meal tests.

3. Introduction

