10.1. Sample Size Determination

An initial 24 patients may be randomized in order that approximately 20 patients complete the study. Twenty completing patients will provide approximately 80% power to demonstrate a 25% decrease in the time to early half-maximal concentration (early 50% T_{max}) between LY900014 and Humalog. Testing will be done at an α -level of 0.1 with a 2-sided confidence interval (CI). The variability was estimated by analyzing internal Lilly data (CCI [REDACTED]) for LY900014 and Humalog administered on CSII therapy, resulting in approximately 35.9% coefficient of variation of within-subject variability for early 50% T_{max} .

Patients who are randomized but drop out before completing assigned treatment may be replaced to ensure that approximately 20 patients complete the study (refer to Section 5.1).

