9.3.2 Pharmacokinetic Statistical Inference

The “PK” population for the statistical inference is defined in Section 8.

Log-transformed insulin lispro T_{max}, early 50% T_{max}, late 50% T_{max}, C_{max}, t_{1/2}, and AUC estimates will be evaluated to estimate geometric means, ratios of geometric means of insulin lispro within LY900014 to Humalog by day and bolus administration mode, and the corresponding 90% CIs of the ratios.

The statistical model for the Day 1 and Day 3 breakfast meal tests will include treatment (4 combinations of treatment and bolus administration mode: LY900014 dual-wave, Humalog dual-wave, LY900014 single-wave, or Humalog single-wave), period, day (Day 1 or Day 3), and treatment-by-day interaction as fixed effects and patient as a random effect.

Example SAS code:

```
proc mixed data=pk;
  class patient treatment period day ;
  model logpk = treatment period day treatment*day / ddfm=kr;
  lsmeans trt*day;
  random patient / grp= treatment;
  repeated / grp= treatment;
run;
```

A separate analysis model will be used for the Day 2 breakfast meal test, including treatment (4 combinations of treatment and bolus administration mode: LY900014 rapid, LY900014 standard, Humalog rapid, or Humalog standard, all given as a single-wave bolus) and period as fixed effects and patient as a random effect.

Example SAS code:

```
proc mixed data=pk;
  class patient treatment period;
  model logpk = treatment period / ddfm=kr;
  random patient / grp= treatment;
  repeated / grp= treatment;
run;
```

For the primary inference, insulin lispro administered from LY900014 will be concluded to have a significantly decreased early 50% T_{max} relative to Humalog if the upper confidence bound of the 2-sided 90% CI of the ratio of geometric means of the early 50% T_{max} is <1 .

If possible, the above models will also be used to calculate the intra-patient and inter-patient variability of LY900014, however if convergence issues occur, then the model will be appropriately updated to account for these issues.

As a sensitivity analysis, early 50% T_{max} will be analyzed by day using the Wilcoxon signed-rank test. The difference in median early 50% T_{max} between LY900014 and Humalog and the 90% CIs for the difference will be presented.

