12.2 Missing Data

Missing data will not be displayed in listings.

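### The plan gives no rule for late 50% Tmax when concentration is still above half of Cmax at 300 min; in dual-wave tests, leaving such values missing can pull the LY900014:Humalog ratio toward 1

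*Protocol*

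**What the plan says.** Protocol section 4 lists late 50% Tmax among the endpoints of the primary objective. The Protocol Synopsis and Protocol 10.3.2.2 put it through a log-scale model, in which "late 50% T_{max} , C_{max} , and AUC estimates will be evaluated to estimate geometric means", with product ratios and 90% confidence intervals. SAP 9.3.2 asks for "ratios of geometric means of insulin lispro within LY900014 to Humalog by day and bolus administration mode".

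At breakfast on Days 1 and 3, the standard dual-wave mode (Mode 1) gives half the bolus at once and "50% as a square wave over 3 hours". The pump keeps delivering the same study insulin as basal, at one hourly rate during the meal test (Protocol 5.1), and the assay measures lispro whatever its source (Protocol 9.5.1). The PK schedule in Protocol section 2 ends with samples at "70, 90, 120, 150, 180, 240, 300" minutes. Lunch and its bolus follow from about 300 min.

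SAP 9.3.1 leaves derivation to standard noncompartmental methods. It names baseline-adjusted PK parameters, with AUC as the example, and does not mention late 50% Tmax there. The SAP abbreviation list describes late 50% Tmax with the definition of the early one. SAP 12.2 reads in full: "Missing data will not be displayed in listings". Completeness rules exist for the exploratory CGM parameters (SAP 9.5.10) but not for PK timing parameters. The Wilcoxon sensitivity analysis covers early 50% Tmax only.

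**The concern.** A profile that is above half of Cmax at 300 min has no observed late 50% Tmax. What is known is that the value is longer than 300 min, or that it does not exist because basal lispro alone holds the level above half-maximum. If the value is left missing, a plain fit to log values drops it, and the dropped values are by construction the longest. The slower product loses more of them, so its geometric mean is shortened more and the ratio moves toward 1. A random patient effect does not repair this, because missingness depends on the unseen value itself.

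Protocol 3.2 gives faster offset as one possible benefit of a new prandial insulin, and late 50% Tmax is the listed parameter that describes offset. A rule chosen later would also be chosen with treatment-level data in view, since the sponsor's team is unblinded during the trial (Protocol 10.3.6, SAP 10).

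**Working it through.** **1. The plan's own figure.** Protocol 10.1: "Twenty completing patients will provide approximately 80% power to demonstrate a 25% decrease in the time to early half-maximal concentration", with within-subject CV 35.9% and two-sided alpha 0.10.
- Effect: −ln(0.75) = 0.2877.
- Log-scale SD: √ln(1 + 0.359²) = 0.3482.
- SE of a within-patient difference: 0.3482 × √(2/20) = 0.1101.
- Noncentral t power with 19 df: 80.9%. The figure is reproduced. It concerns early 50% Tmax; no variability is given for late 50% Tmax.

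**2. Can half-maximum be missed?** For a 10 U dual-wave dose (an example), the immediate 5 U takes 5/1.5 = 3.3 min, so the square wave ends near 183 min. Only the 240 and 300 min samples follow. A two-transit absorption model with steady basal, no basal subtraction and the protocol sampling times (all PK parameters assumed) gives the basal rate, in U/h per U of meal dose, above which the 300 min value exceeds half of Cmax:

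| Single-wave Tmax (min) | Dual-wave threshold | Single-wave threshold |
|---|---|---|
| 71 | 0.12 | 0.37 |
| 54 | 0.26 | 0.56 |
| 42 | 0.41 | 0.78 |
| 32 | 0.58 | 1.07 |

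The documents' only guide to speed is a Humalog peak at 30 to 90 min after subcutaneous doses in healthy subjects (Protocol 3.2). At 10 U and 1.3 U/h (0.13 per U) the slowest profile misses half-maximum at 300 min (true crossing 307 min) and the other three reach it. At 4 U and 1.6 U/h (0.40) the two slower profiles never reach it. With basal subtracted, every typical profile reached it by about 258 min.

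**3. What deletion does to the ratio.** Take late 50% Tmax as log-normal with total log-SD σ, a true ratio r, and values above 300 min deleted. With a = ln(300/geometric mean)/σ for each product and λ(a) = φ(a)/Φ(a), the ratio from all remaining values is r × exp{σ[λ(a_H) − λ(a_L)]}, where H is Humalog and L is LY900014.

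Example: Humalog geometric mean 240 min, r = 0.80 (LY900014 192 min), between-patient log-SD 0.20, within-patient CV 20% (log-SD 0.198), so σ = 0.2815.
- a_H = 0.2231/0.2815 = 0.793: 21% lost, λ = 0.371.
- a_L = 0.4463/0.2815 = 1.585: 5.6% lost, λ = 0.120.
- Observed ratio = 0.80 × exp(0.2815 × 0.250) = 0.86.

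Simulation for r = 0.80, same between-patient SD:

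| Humalog GM (min) | CV | Lost, Humalog / LY900014 | All values | Complete pairs | Likelihood with patient correlation |
|---|---|---|---|---|---|
| 180 | 20% | 3% / 0.5% | 0.82 | 0.81 | 0.81 |
| 240 | 20% | 21% / 6% | 0.86 | 0.83 | 0.85 |
| 270 | 35.9% | 40% / 21% | 0.90 | 0.88 | 0.89 |

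With r = 1.00 the losses are equal and the ratio stays at 1.00. Setting unreached values to 300 min instead of deleting them gives 0.80-0.86 for a true 0.80.

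**4. Whole profiles, with patient variation (all PK assumed).**
- Basal 0.08-0.16 U/h per U of dose, uncorrected: 0.4-30% of Humalog and 0-14% of LY900014 dual-wave profiles are lost. Basal-corrected: 0-5% and 0-1%. The ratio moves toward 1 by under 0.01 up to 0.06, for example 0.80 read as 0.83-0.86.
- Dose 6-16 U, basal 0.6-1.4 U/h, LY900014 absorbed 15-25% faster, uncorrected: 6-37% and 1-19% lost. Corrected: 1-11% and 0-4%. In the slow, 25%-faster, uncorrected case a true 0.81 reads 0.84 (complete pairs) to 0.87 (all values). A censored log-normal fit returns 0.81.
- Extremes at the same doses and basal rates: with a total mean absorption time of 35-50 min, 2.4% or less is lost and the shift is under 0.01. With 35-50 min per absorption stage, uncorrected, up to 57% of Humalog profiles are lost and 0.85 reads 0.93.

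**5. Scale.** If the 35.9% CV is borrowed, the 90% CI half-width for 20 patients is 1.729 × 0.1101 = 0.190 on the log scale, a factor of 1.21. A ratio of 0.80 then has upper limit 0.97; 0.83 gives 1.00; 0.86 gives 1.04.

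**The case against.** The documents are silent on these profiles; they do not prescribe deletion. A reader might infer that late 50% Tmax is analysed only when half-maximum is reached by 300 min. No text says so. SAP 9.3.1 and 9.3.2 plan a half-life and a baseline-adjusted AUC to infinity, so terminal extrapolation is conceivable, as is substitution. Basal correction is also plausible, because samples are taken at −15 and 0 min and baseline-adjusted PK parameters are named; it removes most of the loss. A reader might also take it as fact that mainly Humalog profiles drop out. That depends on basal rate, dose and absorption speed, none of which is given, and on Humalog having the slower offset, which is what the comparison is meant to find out.

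Further, the bias is toward no difference and cannot create a false claim of faster offset. Single-wave tests also measure offset and are little affected (5% or fewer pairs lost). In dual-wave the late fall partly reflects the pump's 3-hour input, so this is not the one place where faster offset would show. SAP 9.1 reports N, so unequal counts would be visible. A censored mixed model with treatment-grouped variances may not be stable in about 20 patients, and where basal alone exceeds half of Cmax a censored model assumes a crossing time that does not exist.

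These points limit the size and shape the remedy. They do not supply the missing rule. N shows that values are absent, not why, and does not correct the ratio; deletion and substitution give different answers; and the completer population in SAP 8 is defined by patient, so it does not settle an undefined parameter in a completed test.

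**Conclusion.** The point holds as a missing derivation rule with a predictable direction of bias if the default is deletion. Under assumed PK the dual-wave ratio is shifted by under 0.01 with fast absorption or basal-corrected profiles, and by about 0.03-0.06 with slow absorption and no correction. Only more pessimistic assumptions, with about 40% or more of Humalog values lost, give 0.08-0.09 or slightly more. The shift requires unequal offset; with equal offset only precision is lost.

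A reader might infer that the primary conclusion is at risk. It is not: the primary inference, the power figure and the sample size all rest on early 50% Tmax. What is exposed is the dual-wave comparison of offset on Days 1 and 3, where a shift of this size can decide whether an interval excludes 1. It should be settled before the data are analysed.

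**What to change.** In SAP 9.3.1, state whether late 50% Tmax is computed on basal-corrected concentrations, and correct its entry in the abbreviation list. Flag each profile that has not fallen to half of Cmax by the last sample, and report the count by product, mode and day.

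In SAP 9.3.2, for the dual-wave comparison, keep the planned model and pre-specify one of these beside it:
- a paired rank analysis that ranks *not reached* as longest, so that a pair with one such value counts as longer for that product and a pair with two is a tie; or
- a log-normal model with a simple random patient effect, with those values right-censored at the actual last sampling time.

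Use the rank version if half-maximum may never be reached or if the model does not converge. Later sampling would not help, because the lunch bolus follows from about 300 min.

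Cost: SAP wording and one extra program, with no new data. The censored interval is slightly wider, and the rank version gives no ratio of geometric means. The censored fit was within 0.005 of the true ratio in simulations of 6,000 patients, but its behaviour with about 20 is untested, so it belongs beside the planned model and should not replace it.
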